11.4 Statistical analysis plan

This section provides a general overview of the statistical analysis plan (SAP). A more detailed SAP will be written by the trial statistician and approved by the TMG and Data Monitoring Committee (DMC) prior to any substantial analysis of the data.

11.4.1 Summary of baseline data and flow of participants

A CONSORT diagram will be produced to report of the flow of participants in the study.

Summary of baseline characteristics, by study arms, will be by frequency and percentage for categorical variables, and for continuous variables by mean and standard deviation (or median and inter-quartile range for non-normally distributed data).

11.4.2 Primary outcome analysis

The threshold for declaring that an education and surveillance plus therapeutic agent(s) arm is superior to education and surveillance plus placebo will be based on the OR for the specific arm compared to education and surveillance plus placebo. The objective is to obtain sufficient certainty (95% at least) that $OR < 1$. In mathematical terms, this quantity is referred to as $P(OR < 1) > 95\%$.

Primary analysis models:

The primary endpoint of incidence of symptomatic laboratory-confirmed COVID-19 infection will be analysed using a Bayesian logistic regression, including as covariates the treatment arm, age (<50 vs. ≥50), and a random effect for site.

The prior distribution corresponding to the education and surveillance plus placebo arm will be such that it is centered on 15% for the event rate, midway between the 5%-25% range that we consider. The prior distribution corresponding to the OR of the treatment arm will be such that the OR is centered on 1. Further details on the prior distributions are provided in the SAP.

Additional multivariable analyses will be conducted, taking into account the following variables: sex, smoking, body mass index, HIV infection, pre-existing respiratory disease, diabetes (recent HbA1c), hypertension, and coronary artery disease.

Secondary outcomes:

The endpoint of severity of symptoms on the WHO scale will be analysed using a Bayesian proportional odds model, using the same adjustment approach as the primary endpoint.

Other secondary outcomes that are binary in nature will be analysed using Bayesian logistic regression, using the same adjustment methods as previously described.

In addition, time-to-event models will be used to assess the effect of the interventions on the time to incidence of symptomatic laboratory-confirmed COVID-19 infection over the 150-day period since receiving trial interventions.

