Main inclusion/exclusion criteria:	
Inclusion criteria
 
 1. Volunteers without clinical evidence of COVID-19 infection aged 18 years and older. 2. Participants who are at high risk of SARS-CoV-2 infection, defined as adults whose locations or circumstances put them at appreciable risk of exposure to SARS-CoV-2 and COVID-19. (see country specific addendum if needed to define further) 3. Must have a mobile phone and access to the Internet for data collection purposes. 4. Participants who are willing and able to provide informed consent via an electronic consent process. 
Exclusion criteria
 
 5. Weight outside range 50 kg – 120 kg (110 lbs – 265 lbs). 6. Self-reported or laboratory confirmed previous or current diagnosis of SARS-CoV-2. 7. Self-reported current acute respiratory infection. 8. Concurrent and/or recent use of the investigational product, a product considered to be equivalent to the investigational product, or any other product that is likely to interfere with the investigational products in this trial or the interpretation of trial data . 9. Self-reported known allergies to any of the IMPs and excipients of the IMPs and placebo. 10. Self-reported presence or history of the conditions listed in the appendices. 11. Self-reported current use of medication with known to interact with any of the medications listed in the appendices. 12. Inability or unwillingness to be followed up for the trial period.
Statistical methods and analysis:	The analysis of the primary endpoint will be by Bayesian logistic regression, adjusting for age as fixed effect, and sites as random effects. The secondary severity endpoint will be analyzed by Bayesian proportional odds model, with the same adjustment strategy. Interim analyses will be performed regularly for efficacy, futility and harm.

3 Background and Rationale

BACKGROUND

A. The Crisis of COVID-19

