This study has several important strengths. Most notably, it is designed to address a clinically highly relevant question with great importance to society. The question is whether interventions can be used preemptively to prevent the occurrence of COVID-19 or to mitigate its severity at risk populations. As a large, pragmatic trial, conducted across multiple continents, this trial will generate precise estimates and generalizable results. Importantly it might provide relevant information for future pandemics as well as the current coronavirus pandemic. There are also important limitations. Event rates (incidence of COVID-19) may vary over time and are somewhat uncertain. These might be higher than anticipated, which would allow the study to reach a conclusion more rapidly, or lower than estimated, which would make this trial too small to detect a difference attributable to the interventions. We plan to increase enrolment at sites where COVID-19 incidence is the highest and decrease enrolment at sites with low event rates. It will be difficult to maintain blinding in this trial. This is especially challenging with a platform design, where arms can be added or dropped. Also

distinct tastes, mode of administration, and side effects of certain interventions can render blinding difficult. The difficulty in including an education and surveillance plus placebo group presents scientific challenges. It is possible that many participants would wish to be assigned to active intervention arms and would be reluctant to take an inert placebo. We aim to address this by conveying to participants the real uncertainty regarding the benefit of prophylactic peri-exposure interventions. Indeed, there is the possibility of harm with any intervention, and a potential of side effects and possibly toxicity with high doses, depending on which intervention is used. We also plan to provide benefit to all participants in the trial through education and improved surveillance of symptoms.

H. Future Directions

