CROWN CORONATION is an international, multi-site trial with sites in Canada, Ghana, India, Ireland, South Africa, UK, USA, Zambia and Zimbabwe. Sites will be selected in settings such as community-based clinics, general practice facilities and hospitals where IRB/REC approval is in place that the study can be conducted there. Access to laboratory testing and a research pharmacy are required. The research site will be associated with a healthcare facility or organization whose staff are considered to be at high risk of contracting COVID-19 and where there are personnel who have received adequate GCP and protocol training and are able to conduct the study procedures. Preferably, each site should be able to recruit at least 20 participants during the trial period although in rural locations, this number may be smaller. Consideration will also be given to whether there has been a report of COVID-19 outbreak in the local area, as this will increase the risk of individuals contracting the disease.

Participants

Participants will include adults (18 years or older) who are at risk for contracting SARS-CoV-2 based on their work in hospitals or in the community. See the country-specific addenda for country-specific definitions of individuals at risk for SARS CoV-2 exposure.

The reason that participants are at risk will be recorded in the CRF. Participants will be enrolled in low, middle, and high-income countries, including, Canada, Ghana, India, Ireland, South Africa, UK, USA, Zambia and Zimbabwe. Other countries may be added with time. All participants will be fully informed about the trial and will provide informed consent (electronically).

Baseline Data

At the time of enrolment, demographic information will be collected from participants, and relevant data on their medical histories, comorbidities, concurrent medication, and risk factors for severe COVID-19 will be documented. They will also provide information on the nature of their work and the contexts in which they are likely to encounter people infected with SARS-CoV-2. They will also provide information on their access to and use of personal protective equipment during high-risk encounters. In addition, they will be asked to nominate at least one other person to contact in case they become unwell so that we can establish what happened to them. This will all be done in line with local data protection legislation.

Interventions

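### The primary model adjusts for age group and site only and leaves recorded baseline exposure unused; the cost is a small loss of precision, not bias

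*Combined protocol and SAP*

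**What the plan says.** The primary endpoint, symptomatic PCR-confirmed COVID-19 by day 60, is analysed in Section 11.4.2 by "Bayesian logistic regression, including as covariates the treatment arm, age" group and a random site effect. The Section 2 summary agrees: "adjusting for age as fixed effect, and sites as random effects". Section 11.4.2 carries the same adjustment over to the severity scale and the other binary outcomes.

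Section 5.1 (Participants; Baseline Data) lists what is recorded about exposure:
- "The reason that participants are at risk will be recorded in the CRF"
- "information on the nature of their work and the contexts in which they are likely to encounter people infected with SARS-CoV-2"
- "access to and use of personal protective equipment during high-risk encounters"

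None of these is in the primary model, the additional multivariable model or the subgroup list of Section 11.4.3. The additional model uses "sex, smoking, body mass index, HIV infection, pre-existing respiratory disease, diabetes (recent HbA1c), hypertension, and coronary artery disease".

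On calendar time, Section 3 (G, Strengths and Limitations) says "Event rates (incidence of COVID-19) may vary over time and are somewhat uncertain". Section 11.3 provides permuted blocks, 1:1 at the start, stratified by age and site. Section 11.5 restricts comparisons for an added arm to concurrent controls.

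**The concern.** The endpoint is the acquisition of a symptomatic infection. Of the baseline data collected, job type, contact setting and protective equipment lie closest to that risk. The covariates in the additional model are mostly comorbidities instead. Adjusting a logistic model for a prognostic baseline variable raises the power of the treatment test, and here the data would be in hand at no extra cost. At the lowest control rate considered, planned power is only just above 80%, so even a small gain has some use.

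The additional model raises a smaller wording question. HbA1c is named there and nowhere else in the supplied text.

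**Working it through.** **Inputs.** Control rate 5%, OR 0.7, up to 2,500 per arm and the rule P(OR<1) > 95% are from Section 11.2.1. Under a vague prior the rule is close to a one-sided 5% test (critical value 1.645). The strength and prevalence of the exposure factors are assumptions, because the documents give none.

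**1. The plan's own figure.** Treated odds = 0.7 × 0.05/0.95 = 0.03684, so treated risk = 0.03684/1.03684 = 3.55%.

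SE(log OR) = √[1/(2,500 × 0.05 × 0.95) + 1/(2,500 × 0.0355 × 0.9645)] = 0.1417

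z = 0.3567/0.1417 = 2.516; power = Φ(2.516 − 1.645) = 80.8%

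A two-proportion formula gives 81.2% and a beta-binomial simulation 80.7%. The stated power above 80% therefore reproduces at 2,500 per arm (at 2,000 it is about 73%).

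**2. Gain from adjustment.** Take two independent binary baseline factors, 50% prevalence each, and hold the marginal OR at 0.70. The adjusted SE comes from the inverse of the logistic information matrix for intercept, arm and both factors. Information gain = (z adjusted / z unadjusted)² − 1.

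| Assumed ORs | Conditional OR | Adjusted SE | z | Information gain | Power |
|---|---|---|---|---|---|
| none | 0.700 | 0.1417 | 2.516 | – | 80.8% |
| 1.5 and 1.5 | 0.699 | 0.1420 | 2.520 | 0.3% | 80.9% |
| 2 and 2 | 0.698 | 0.1424 | 2.528 | 1.0% | 81.1% |
| 3 and 4 | 0.693 | 0.1438 | 2.553 | 2.9% | 81.8% |

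In participants this is 0.003 × 5,000 = 15 up to 0.029 × 5,000 = 145. At 20–30% prevalence the range is 0.3% to 4.0%. For ORs of 3 and 4, simulated trials gave information gains of 2.9%, 5.5% and 8.0% at control rates of 5%, 10% and 15%. Power at 10% and 15% with 2,500 per arm is already about 97% and 99%, so the larger gain matters less there.

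**3. A more favourable assumption.** Suppose one perfectly measured normal risk score and a conditional OR of 0.7. At log-odds SDs of 0.5, 1.0 and 1.5, power moves from 80.1% to 80.5%, 77.5% to 79.3% and 72.0% to 76.9%. An SD of 1.5 means odds differing by e³, about 20-fold, between people one SD above and one SD below the mean. A coarse category would not capture all of that.

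**4. Validity.** Null trials were simulated (10,000 per setting) with 1:1 allocation in blocks and with exposure and period effects both left out of the analysis. False declarations were 4.8% with no such effects, 5.2% at SD 1.0 and 4.7% at SD 1.5. The Monte Carlo error is √(0.05 × 0.95/10,000) = 0.2 points, so no inflation is visible.

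**5. When period would matter.** Section 11.3 fixes 1:1 only at the start. Assume 5,000 participants at 1:1 with a 5% rate, then 5,000 at 2:1 (active to control) with 10%, no treatment effect and no period term:
- active: (125 + 333)/5,833 = 7.86%
- control: (125 + 167)/4,167 = 7.00%
- pooled OR = 1.13 instead of 1

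**6. How fine a period term can be.** Expected first-phase events are 125 + 89 = 214. Section 11.2.2 estimates 12 months of recruitment and Section 5.1 names nine countries. Two-month bands by country make 6 × 9 = 54 cells, about 4 events each, which is too sparse.

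**7. HbA1c.** Sections 5.1 and 8.1 list medical history and comorbidities. Sections 8.5 and 8.6 list nasal swabs and dried blood spots for serology. HbA1c is in neither list; diabetes can be taken from the history.

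**The case against.** The strongest reply is that this is a matter of preference. Blocking within site and concurrent controls protect the comparison, the gain depends on assumed odds ratios, and the calculation in step 2 starts from a model without site or age. Site may already carry part of local exposure and timing. At-risk definitions are country-specific, so no common exposure category is shown to exist. Section 11.4 also defers details to a fuller SAP.

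Most of this stands, and it limits the size. It does not remove the point. Site cannot separate exposure levels within a site. Section 5.1 prefers at least 20 participants per site, which at 5% is 20 × 0.05 = 1 expected event, so many site effects would be heavily shrunk.

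Three stronger readings are tempting, and the documents do not support them:
- A reader might infer that omitting exposure or period biases the result, or that a constant site effect requires stable risk at each site. Under 1:1 blocks within site the comparison needs neither. Moving enrolment towards high-incidence sites is largely a between-site change, which the site effect takes up.
- A reader might infer that enrolment period is a recorded covariate left out of the model. No section lists it, although online randomization dates every participant.
- A reader might infer that the additional model would shrink to people already tested for diabetes. No section specifies a complete-case fit, the bracketed HbA1c may only define diabetes, and the schedule of evaluations (Appendix 1) was not available.

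**Conclusion.** A minor improvement to the plan, not a defect in validity. Recorded baseline exposure enters no listed model, and using it would add about 0.3% to 2.9% information, or 0.1 to 1 power point, at a 5% control rate and 2,500 per arm. This rests on two assumed binary factors at 50% prevalence and a comparator without site or age. A single factor, or the planned model with site as comparator, would give less; much stronger prognostic effects would give more. With 1:1 blocked allocation there is no bias to correct. A period term becomes a safeguard only if the allocation ratio changes and phases are pooled. The HbA1c point touches a supportive model only and is limited to the supplied text.

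**What to change.** In Section 11.4.2 and the detailed SAP:
- Add one coarse baseline exposure category to the primary model, defined identically across countries from the work, contact-setting, protective-equipment and reason-at-risk items. Use baseline values only. The contact counts logged during follow-up (Section 16) arise after randomization and should not be used.
- Optionally add a coarse calendar-period term, for instance quarters of the enrolment year (about 214/4 ≈ 54 events each), without region-by-period cells.
- In the additional model, define diabetes from the collected medical history, without requiring a recent HbA1c.

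The cost is SAP wording, agreement on a harmonised category and a few more parameters. The reported OR becomes conditional on exposure and lies slightly further from 1 (0.693 for a marginal 0.70 in the strongest case tabulated). The SAP should therefore say that the OR thresholds in Section 11.5 apply to this adjusted OR.

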11.4.3 Sensitivity and other planned analyses

Subgroup analyses will be pre-specified and performed using an interaction term in the model between the treatment arm and the characteristics of interest. The factors of interest are: age, HIV status, geographic region, ethnicity and sex.

11.5 Interim analyses

This Bayesian trial will perform frequent interim analyses for efficacy, futility and harm. This means that the DMC will regularly consider the balance of benefit and risk. Strong evidence of benefit, futility, or harm will result in the advice to modify or stop the trial.

The objective of interim analyses is two-fold: 1/ identify whether an active arm is futile, if the probability that its $OR \geq 0.9$ is high, greater than 95%, 2/ identify whether there is sufficient evidence that an active arm is superior to the control arm. The following table contains the statistical triggers for efficacy, futility and harm at interim analyses and for the final analysis.

Probability	Threshold at interim analysis	Threshold at final analysis	Evidence for:
$P_1 = P(OR < 0.8 \mid \text{data})$	99%	95%	Marked clinical benefit
$P_2 = P(OR \geq 0.9 \mid \text{data})$	99%	95%	Non clinically relevant (i.e. futile) treatment (or harm when $OR \geq 1$)

Posterior predictive probabilities will also be calculated at each interim analysis to inform the potential adaptation decisions.

Platform trial

In the study there exists a possibility of adding treatment arm(s) at interim analysis or during the course of the study. If a treatment arm is added, all comparisons will be made with concurrent control participants.

For the main effects of individual treatments (i.e. when given on their own), the thresholds for superiority and futility described above will apply to the same manner to the additional treatment(s).

For treatments that are given in combination in the context of a potential factorial design, the quantity of interest will be $P(\text{interaction term} < 1 \mid \text{data}) \geq 0.95\%$ (or 99% at interim analysis) to declare evidence of synergy. The prior distribution for the interaction term will be specified in exactly the same way as the prior of the OR of the individual treatments. Only its interpretation changes.

The SAP contains additional details regarding the monitoring of the trial, including the cumulative probability of declaring efficacy depending on the underlying simulated hazard ratio.

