11.2 Sample size and recruitment

11.2.1 Sample size calculation

We considered different event rates, depending on the following assumptions. Firstly, we assumed that 30-50% of the participants may become infected with SARS-CoV-2 over the course of the study period. Of these, the percentage of participants who will experience the primary endpoint or laboratory test-confirmed symptomatic COVID-19 (i.e. any of the following: cough, shortness of breath or difficulty breathing, fever, chills, muscle pain, sore throat, new loss of taste or smell, nausea, vomiting, or diarrhea) is uncertain. We use a range of 15-50%. The estimated event rate is therefore $0.15 * 0.30 = 0.045$ (or 4.5%, rounded to 5%) to $0.50 * 0.50 = 0.25$.

We declare the superiority of a treatment arm if the probability that the Odds Ratio (OR) of the treatment is less or equal to 1 is greater than 95%, i.e. $P(OR < 1) > 95\%$. The remaining Bayesian statistical triggers of the adaptive trial are specified in section 11.5.

A 2-arm trial was simulated to assess the required sample size for the study. The OR was assumed to be 0.7. Three event rates for control arm were used: 5%, 10% and 15%. We are interested in the lower end of the 5-25% range for the control rate since a higher sample size is required when the event rate in the control arm decreases for a given effect size.

Figure 5 below reports the probability that the simulated trial concludes superiority of the treatment arm depending on the sample size per arm.

[figure not shown]

Figure 5: Sample size estimation for the first phase of the trial (2-arm)

The simulations show that the probability of declaring efficacy depends on the event rate in the placebo arm. With 2000-2500 participants per arm, even if the event rate is 5% in the control arm, the study has >80% chance to declare efficacy.

We propose to retain the option of reaching a maximum of 2,500 participants per arm. We will aim to enrol a maximum of 5,000 participants in total in the first phase of the trial to allow for possible loss-to-follow-up (LTFU), withdrawal, protocol deviation, non-adherence and other methodological challenges. Further phases may be added to the trial until a maximum of 30,000 participants is reached.

The assumptions underlying the sample size calculations will be reviewed at each interim analysis based on the observed data.

11.2.2 *Planned recruitment rate*

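### Section 11.5 gives the interim futility threshold as 95% in the text and 99% in the trigger table, and prints the final synergy threshold as 0.95%, very probably a slip for 95%

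*Combined protocol and SAP*

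**What the plan says.** **Futility.** Section 11.5 describes two aims of the interim analyses. The first is to "identify whether an active arm is futile, if the probability that its" odds ratio is 0.9 or more "is high, greater than 95%, 2/ identify whether there is sufficient evidence that an active arm is superior to the control arm". The section continues: "The following table contains the statistical triggers for efficacy, futility and harm at interim analyses and for the final analysis". In that table the row for P2 = P(OR ≥ 0.9 | data), labelled "Non clinically relevant (i.e. futile) treatment (or harm when" the OR is 1 or more), has 99% in the interim column and 95% in the final column.

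**Synergy.** Under the platform heading of Section 11.5, combinations in a factorial phase are judged on the posterior probability that the interaction term is below 1. The final criterion is printed as at least 0.95%, followed by "or 99% at interim analysis) to declare evidence of synergy". On the prior, the section states: "The prior distribution for the interaction term will be specified in exactly the same way as the prior" of the individual treatment ORs. Section 11.4.2 says that this treatment prior "will be such that the OR is centered on 1".

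**Where a reader is sent.** Section 11.2.1 says: "The remaining Bayesian statistical triggers of the adaptive trial are specified in section 11.5". Section 8.11 (Stopping Rules) gives no numbers. Sections 11.4, 11.4.2 and 11.5 mention a more detailed SAP, which is not among the documents available for this review.

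**The concern.** The Summary (Section 2, Type of trial) says that the trial will be adapted early against thresholds set in advance. For interim futility, two values are printed for one quantity at one decision point, in the section to which Section 11.2.1 sends the reader. Section 11.5 also carries its superiority and futility thresholds over to treatments added later, so the ambiguity goes with them. If it is still open at the first look, the choice could be made after the data have been seen.

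The synergy figure is a different kind of defect. A posterior probability of 0.0095 that the interaction OR is below 1 is strong evidence against synergy, so a rule that declares synergy at or above that value cannot do its job. It matters only once a factorial phase opens, and only if it is programmed as printed.

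**Working it through.** The plan gives no figure to reproduce here, so the first step is to compare the printed values.

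| Quantity | Stage | Running text | Table |
|---|---|---|---|
| P(OR ≥ 0.9) | interim | > 95% | 99% |
| P(OR ≥ 0.9) | final | not stated | 95% |
| P(interaction < 1) | interim | 99% | not in table |
| P(interaction < 1) | final | ≥ 0.95% | not in table |

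The futility sentence attaches the table's final value to interim looks.

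**Inputs from the plan:** control rates of 5% and 15% (from the 5%, 10% and 15% in Section 11.2.1); design OR 0.7; at most 2,500 per arm in the first phase; 10,000 further participants in the four-arm phase (Section 3), so 10,000/4 = 2,500 per cell.

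**Assumptions:** a flat prior, because only the prior's centre is given; look times, because the plan says only that looks are frequent; single-agent ORs of 0.8 for the synergy check.

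**Futility, one look at 1,250 per arm.** With a normal approximation to the posterior of log OR, the arm is flagged when the estimated log OR exceeds ln 0.9 + z × SE, where SE² = 1/[n·pc(1 − pc)] + 1/[n·pt(1 − pt)] and pc and pt are the control and treated event rates. At a true OR of 1.0:

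- 5% control rate: SE = √[2/(1,250 × 0.05 × 0.95)] = 0.1835.
  - 95%: −0.1054 + 1.645 × 0.1835 = 0.197, so the observed OR must exceed 1.22. Chance = 1 − Φ(0.197/0.1835) = 14.2%.
  - 99%: −0.1054 + 2.326 × 0.1835 = 0.322, so the observed OR must exceed 1.38. Chance = 4.0%.
- 15% control rate: SE = 0.112, and the chances are 24.1% and 8.3%.

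**Futility, any of three looks (625, 1,250, 1,875 per arm).** Simulated binomial counts, at least 200,000 trials per scenario, 0.5 added to each cell:

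| True OR | 5% control: 95% vs 99% | 15% control: 95% vs 99% |
|---|---|---|
| 0.7 | 0.7% vs 0.1% | 0.1% vs 0.01% |
| 0.8 | 3.0% vs 0.4% | 1.2% vs 0.2% |
| 0.9 | 10% vs 2% | 10% vs 2% |
| 1.0 | 25% vs 8% | 40% vs 16% |
| 1.2 | 71% vs 42% | 96% vs 85% |

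At a 5% control rate the two readings disagree in 8%, 17% and 28% of trials at ORs of 0.9, 1.0 and 1.2. Replacing the flat prior with one centred on OR 1 with an assumed SD of 0.5 on the log scale changes little: 24% vs 7% at OR 1.0, and 70% vs 40% at OR 1.2.

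**Synergy.** Before any data, a prior centred on 1 gives P(interaction < 1) of about 0.5, which already exceeds 0.0095. At one final look with no true interaction, the chance of declaring synergy is 1 − threshold: 1 − 0.0095 = 99% as printed, and 1 − 0.95 = 5% at 95%. Simulation with 2,500 per cell gives the same 99% and 5%. Under true antagonism, the literal rule declares synergy as follows:

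| Interaction OR | 5% control | 15% control |
|---|---|---|
| 1.25 | 89% | 68% |
| 1.5 | about 60% | 13% |
| 2.0 | 9% | under 0.1% |

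**The case against.** Section 11.5 largely settles the futility point itself: the 95% sits in a sentence about aims, while the table is introduced as holding the triggers and has separate interim and final columns. A statistician implementing the plan would probably use 99%. That is the natural reading, but nothing in the documents says that the table prevails, and the sentence is itself worded as a rule.

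The readings also differ mainly where flagging is appropriate. At ORs of 1.0 and 1.2 a higher crossing rate is earlier correct flagging, and at the design OR of 0.7 both readings rarely flag the arm. This stands, and it limits the harm to effective arms. It does not remove the difference in when an arm with little or no benefit is flagged.

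The rates depend on assumed looks. They also leave out the posterior predictive probabilities that Section 11.5 adds and the advisory role of the DMC, so they are illustrative. The synergy rates suppose that someone programmes an implausible threshold, which a statistician would probably notice; taken alone, that item is a typographical correction.

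Finally, Section 11.4 has the detailed SAP approved by the TMG and DMC before substantial analysis. That lowers the practical risk, but a correct SAP would still leave the protocol contradicting itself.

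**Conclusion.** Both points hold and should be fixed; confidence is high. The interim futility threshold has two printed values. Under the assumed three looks, the choice changes the chance of a futility flag at OR 1.0 from 25% to 8% (5% control rate) or from 40% to 16% (15% control rate), with little effect at OR 0.7. The inconsistency itself rests on no assumption; only these rates depend on look times, prior width and the normal approximation.

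The printed 0.95% cannot serve as a synergy criterion. The 99%/95% pairing in the table and the 95% superiority rule in Sections 11.2.1 and 11.4.2 make 95% the very probable intent. The futility conflict carries most of the weight. Whether the detailed SAP states either value correctly is unknown.

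**What to change.** Before the first interim analysis, make the futility sentence in Section 11.5 agree with the table. The simplest edit is for the sentence to refer to the table's thresholds (99% interim, 95% final). If 95% at interim was intended, change the table instead; the sponsor should confirm which. Print the synergy criterion as P(interaction OR < 1 | data) ≥ 95% at the final analysis and 99% at interim. Use the same values in the detailed SAP and in the operating-characteristic simulations.

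The cost is a short wording amendment, with ethics and regulatory approval where Section 15 requires it. The simulations need rerunning only if they used a different value.

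### The final efficacy rule is stated two ways, P(OR<1)>95% and P(OR<0.8)>95%; the >80% power holds only for the first and is about 24% for the second at the same 5% control rate

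*Combined protocol and SAP*

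**What the plan says.** Section 11.2.1 gives the rule used to size the trial, with a 95% threshold: "We declare the superiority of a treatment arm if the probability that the Odds Ratio (OR) of the treatment is less or equal to 1". The effect is fixed there ("The OR was assumed to be 0.7"), control rates of 5%, 10% and 15% are considered, and the result is: "With 2000-2500 participants per arm, even if the event rate is 5% in the control arm, the study has >80% chance to declare efficacy". The section then adds: "The remaining Bayesian statistical triggers of the adaptive trial are specified in section 11.5".

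Section 11.4.2 repeats the rule for the primary analysis: "The objective is to obtain sufficient certainty (95% at least) that" the OR is below 1.

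Section 11.5 introduces its table with: "The following table contains the statistical triggers for efficacy, futility and harm at interim analyses and for the final analysis". The table has two rows. The benefit row is P(OR<0.8 | data), with thresholds of 99% at interims and 95% at the final analysis, and is labelled as evidence of marked benefit. The other row is P(OR≥0.9 | data), for futility or harm. P(OR<1) for the effect of a single treatment does not appear in 11.5. On arms added later, the section says that "the thresholds for superiority and futility described above will apply to the same manner to the additional treatment(s"; within 11.5, the only thresholds this can refer to are those around the table.

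**The concern.** This is the decision rule for the primary endpoint, so it must have one reading. As written, the same final data can be superior under 11.4.2 and miss the efficacy trigger in 11.5. A trial that observed exactly the planned OR of 0.70 at a 5% control rate would do this.

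If 11.5 governs, the stated power does not apply to the rule in force, and the trial is badly underpowered at its own planning effect. If 11.4.2 governs, the table misdescribes the final analysis. Until this is settled, the choice between the rules could be made after the data are seen. The DMC and every added arm inherit the same ambiguity.

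**Working it through.** **Inputs.** From 11.2.1: OR 0.7; control rates 5%, 10% and 15%; at most 2,500 per arm. From 11.3: 1:1 allocation. From 11.4.2: a prior on the treatment OR centred on 1, with no spread given here. I assume a vague prior first and then vary it. No dropout rate is given, so none is applied.

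**Formula.** With a vague prior, P(OR<c | data)>95% is met when the estimated log OR lies at least 1.645 standard errors below ln c. The probability of meeting it is therefore about Φ(ln(c/0.7)/SE − 1.645), where SE² = 1/[n·pc(1−pc)] + 1/[n·pt(1−pt)].

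**Treated rate and SE at a 5% control rate.** The treated odds are 0.7 × 0.05/0.95 = 0.0368, so pt = 3.55%. With n = 2,500, SE = √(1/118.75 + 1/85.7) = 0.1417.

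**The plan's own figure, rule OR<1.** Φ(0.3567/0.1417 − 1.645) = Φ(0.87) = 80.8%. A one-sided two-proportion calculation gives 81.2%, a 200,000-trial simulation 81.1%, and a Beta-posterior simulation of 4,000 trials 80.3%. This reproduces the >80% claim at 2,500 per arm. At 2,000 per arm it is about 73%, and about 2,440 per arm are needed for 80%, so the claim holds only near the top of the quoted range.

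**The 11.5 trigger, rule OR<0.8.** Φ(0.1335/0.1417 − 1.645) = Φ(−0.70) = 24.1% (simulation 23.7%, Beta posterior 23.8%).

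**Across control rates (2,500 per arm, OR 0.7, single final look):**

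| Control rate | SE | P(OR<1)>95% | P(OR<0.8)>95% |
|---|---|---|---|
| 5% | 0.142 | 81% | 24% |
| 10% | 0.102 | 97% | 37% |
| 15% | 0.085 | 99.5% | 47% |

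At 25%, the top of the range in 11.2.1, the second rule reaches about 62%.

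**Size needed for 80% under OR<0.8 at a 5% control rate.** (2.4866/0.1335)² × [1/(0.05×0.95) + 1/(0.0355×0.9645)] ≈ 17,400 per arm. That is about 34,800 in two arms, above the 30,000 maximum for the whole platform.

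**What must be observed (5% control rate).** The estimated OR must be at most about exp(−1.645×0.1417) = 0.79 under the first rule, and at most about 0.8×0.79 = 0.63 under the second.

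**Effect of the prior (5% control rate, 2,500 per arm).** With normal priors on the log OR centred at 0 and SD 1, 0.5 or 0.35, the OR<0.8 probability falls to 22%, 18% or 13%. The OR<1 probability falls only to 81%, 79% or 77%. The vague prior is thus the favourable case for the 11.5 rule.

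**With interim looks.** The plan fixes no schedule, so I assumed looks at 625, 1,250, 1,875 and 2,500 per arm, with early stopping for efficacy at P(OR<0.8)>99% and a 5% control rate. About 9% of trials stop early for efficacy. Total success, early stops included, is 81% if the final rule is OR<1 and 25% if it is OR<0.8. In about 56% of all trials the final data meet the first rule and fail the second.

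**The case against.** The best defence is that two tiers were meant. Section 11.2.1 sends the reader to 11.5 for the remaining triggers, which suggests additions to the superiority rule and not a replacement. The table labels its benefit row as marked benefit, and two sections agree on OR<1. On that reading a higher tier need not be powered, and the repair is mostly relabelling. This reading is possible, but no section states it. Section 11.5's own words point the other way: they present the table as the efficacy triggers for the final analysis and then speak of thresholds for superiority.

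Three further points are fair. The 24% belongs to the lowest control rate considered and rises with that rate; but it is the same rate to which the plan attaches its >80% claim. The prior spread is unknown here, although tighter priors centred on 1 lower the figure. The plan also promises a more detailed SAP, which may settle the matter; it would still leave the protocol contradicting itself.

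**Conclusion.** The concern holds and must be fixed. The final efficacy criterion for the primary endpoint is stated in two incompatible ways, and the stated power belongs to only one of them. At the plan's own 5% control rate the probability of success is about 81% under OR<1 and about 24% under OR<0.8. At a 15% control rate the figures are 99.5% and 47%. They assume a true OR of 0.7, 2,500 per arm, a vague prior, no attrition and a single final look. The 56% disagreement also depends on the assumed interim schedule. That the trial is underpowered is conditional on the 11.5 trigger governing; that the rule is not uniquely defined is not conditional.

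**What to change.** State one final efficacy criterion, in the same words, in 11.2.1, 11.4.2 and 11.5. I suggest P(OR<1 | data)>95%, since the stated power follows from it. In the 11.5 table, keep P(OR<0.8)>99% as the interim trigger for early efficacy. Relabel the final-analysis P(OR<0.8)>95% cell as a supplementary description of marked benefit that does not decide efficacy. Make the sentence on added treatments point to the same criterion.

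Then report the probability of success for the combined interim and final rules, with the prior and interim schedule stated, and limit the >80% claim to the sample size at which it holds.

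If the sponsor does intend OR<0.8 to decide the final analysis, change 11.2.1 and 11.4.2 to match and replace >80% with about 24% at a 5% control rate, or revisit the sample size.

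The suggested route costs protocol and SAP wording and one re-run of the simulation, with no extra participants. Keeping OR<0.8 with 80% power at a 5% control rate would need about 17,400 per arm.
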